1.0 Objectives

Primary: To use a pragmatic **phase II randomized controlled trial** to compare two standardized bundles of usual care for postoperative pain management to reduce the initial discharge prescription opioid volume.

Secondary: To assess which pragmatic arm improves aspects of postoperative recovery including 30-day, 3-month, and 1-year opioid use, patient symptom inventory at those time points, hospital measures including length of stay and inpatient pain scores.

The **primary aim** of this proposal is to use a pragmatic **phase II randomized controlled trial** to compare two standardized bundles of usual care for postoperative pain management. One arm has the **intervention of an intraoperative plus second regional anesthetic block (QL block) versus a comparison/control** arm of a single intraoperative QL block, **both bundled** with a standardized non-opioid pain management protocol, to **decrease the initial discharge prescription opioid volume for retroperitoneal sarcoma survivors** after potentially curative surgery. The primary outcome measure will be the initial discharge opioid prescription (oral morphine equivalents, OME) of patients in each arm. **Both arms will include a standardized non-opioid bundle** for pain control supplementation during hospital stay and upon discharge and previously published enhanced surgical recovery protocols, based on clinically relevant preoperative strata.

PICO: In patients undergoing open retroperitoneal/intra-abdominal sarcoma resection using general anesthesia with regional pain block (QL block with 72-hr liposomal bupivacaine) **[Patients]**, can the placement of a 2nd QL block on postoperative day 4 (“Rescue” block **[Intervention]**) more effectively wean patients off postoperative opioids during the inpatient stay vs. usual care of QL block (both arms with low-dose IV-PCA plus non-opioid bundle) **[Comparison/Control]**. The primary outcome measure will be the initial discharge opioid prescription volume of patients in each arm **[Outcome]**.

Outcome Measures:

Primary:

- **Initial discharge prescription OME [continuous variable]**

Secondary:

- **Hospital Measures**

- Proportion of patients with discharge prescription OME = zero
- Patient Reported Outcomes for gastrointestinal surgery– MD Anderson Symptom Inventory (MDASI-GI)
- Daily inpatient pain scores
- Total length of stay and cost

- **Discharge Measures**

- 30-day total OME
- Initial discharge Rx volume <200mg (Y/N)

- Number of postoperative days until zero opioid use
- Opioid use at 30 days, 3 months, and 12 months (Y/N, OME)
- MDASI-GI at 30 days, 3 months, and 12 months
- 3-mo and 1-yr follow-up – patients free of opioid use (Y/N)

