We thus see an opportunity to accelerate postoperative opioid weaning to reduce the total opioids used in the postoperative setting with the downstream effect of having less patients using opioids past the initial recovery period (characterized in literature as “persistent use”). We hypothesize that a second, repeat QL block on postoperative day 4 will bridge the gap between the initial intraoperative QL block and ambulatory status, reduce the total postoperative OME, and increase the proportion of sarcoma survivors free of opioids beyond the postoperative recovery period. **“Rescue blocks” are currently used on an as-needed basis** only when the first block is insufficient or if the clinical team decides that the opioid use is subjectively too much. Until recently with our **“RESQU-BLOCK” trial** (PA18-0859, NCT03745794), we had not been routinely using a 2nd block, because opioid-free discharge has never previously been a goal, even with enhanced surgical recovery protocols. However, with the successful implementation and enrollment of the RESQU-BLOCK trial (similar goals as this trial except in pancreatectomy, with first enrollment 3/1/2019), our new long-term goal is to **reduce dissemination of opioids into the community and reduce the risk of persistent opioid use among survivors, their families, and their communities.**

“Enhanced recovery after surgery,” or ERAS, is no longer a novel idea. However, its benefits are beginning to be seen beyond the early metrics of hospital stay and activities of daily living. Downstream benefits have included reduced complications, fewer readmissions (despite earlier discharges), less hospital resource consumption (cost), and improved postoperative quality of life. With the opioid epidemic increasingly discussed in both medical

and lay literature, we are seeking to modify our enhanced recovery program in abdominal cancer surgery to reduce opioid exposure in the hospital. Medical literature has shown that oftentimes the first exposure or greatest exposure to opioids comes from an elective surgical event. Persistent opioid use can be predicted by the size of a patient's initial outpatient prescription **oral morphine equivalents (OME)** and the initial outpatient prescription OME can be predicted by the amount of opioids used in the last 24hrs of hospitalization, which is often the result of how quickly the inpatient pain medications are weaned.

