4.0 Research Plan and Methods

This is a **single-center pragmatic phase II open-label randomized controlled trial** to compare two standardized bundles of usual care for postoperative pain management. The single difference in intervention is an additional QL block on POD4 in patients undergoing sarcoma surgery with potentially curative intent. The **primary endpoint is the initial discharge prescription OME**. Patients will be randomized with 1:1 ratio to receive either QL in OR + non-opioid bundle +/- low-dose IV-PCA (control arm) or QL in OR and QL on POD4 AM + non-opioid bundle +/- low-dose IV-PCA (experimental arm). The **randomization will occur on postoperative day 3** so that usual care will be performed intraoperatively and for the first 3 days after surgery. On POD3, at the time of randomization, patients will be stratified based on preoperative use of long-term opioids (e.g. extended or continuous release) (yes vs. no) and preoperative average daily OME use ($>7.5\text{mg}$ vs. $\leq7.5\text{mg}$ OME, which allows 1 tramadol, 1 oxycodone, or 1 hydrocodone per day in the lower stratum) in the 7 days before surgery. Patients will further be stratified by whether they undergo nephrectomy (yes vs. no) as part of their operative procedure, or if they have a previous surgical history of nephrectomy, as this would impact their eligibility for some of our frequently used adjunct pain medications (e.g. Celebrex, Toradol). There will be no standardization of postoperative dietary advancement, fluid management, or postoperative care, other than standardization of the IV and oral non-opioid bundle and initial IV-PCA settings in the recovery room on POD0.

Method of Group Assignment and Randomization

- **Stratified Randomization:** REDCap will be used for 1:1 allocation and stratification for preoperative long-term (≥ 3 months) opioid use (yes vs. no), preoperative average daily OME use ($>7.5\text{mg}$ vs. $\leq7.5\text{mg}$ OME), and nephrectomy status (yes vs. no), as detailed above.
- **Implementation:** Acute pain team, surgeons, advanced practice providers, fellows, and nurses will perform interventions and assessments per usual care.
- **Blinding:** This is an open-label study since the intervention arm will receive a 2nd QL block which cannot be blinded from the patient or treating physician. The allocation will be unmasked immediately upon randomization on POD3 morning after clinician rounds.

Intervention Strategy:

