 - **Dosage instructions in Figure 3 below.** The Operating Room pharmacy has calculated the appropriate max dose of long-acting and short-acting bupivacaine, which can be safely mixed. There are laminated placards in every operating room as protective measures to prevent dosage miscalculations, and most nurses know the mixture. The Acute Pain Service attendings know as well since they have performed thousands of these injections in the past few years at our institution.
 - **Liposomal bupivacaine has become our standard of care for open surgery.** We use this in the majority of our open abdominal cancer surgery patients, while an ever-decreasing minority still get epidurals. There is extensive experience using liposomal bupivacaine for regional blocks. This RCT does not focus on the use of the block per se (since it is routine or usual care), but rather the timing of it.

Comparison Strategy:

The comparison arm patients will have usual care with just the single QL using ultrasound guidance placed in the OR. When the liposomal bupivacaine wears off, **there will be no second QL block.** The **usual measures of non-opioid bundle** [including acetaminophen, NSAIDs, muscle relaxers] and conversion from IV pain meds to oral pains will be done to reduce total opioid exposure and use.

Decision on Discharge Opioid Prescription

To avoid bias in one arm or the other, all discharge prescriptions will be standardized. Both arms will get standard non-narcotic bundles of acetaminophen 650mg q6hrs, celecoxib 100mg q12hrs, and methocarbamol 250-500mg q8hrs. Slight dose variations can be allowed here based on pharmacy availability (e.g. recent national shortage of methocarbamol 500mg pills). Patients who undergo nephrectomy will not receive celecoxib due to risk of renal insufficiency. To standardize the opioids, we will use a multiplier of 5x the last-24hrs OME count. This 24-hr count can be easily found in the electronic health record and will be taken from the time of final discharge prescription writing. If this is POD4, it will be calculated after the 2nd block, if one is administered. We chose 5x because the CDC recommends 7 days max prescription and less than 200mg OME. All patients have

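### No outcome measures daily or cumulative inpatient OME after randomisation, so a difference in discharge OME cannot by itself be read as faster inpatient weaning rather than a different discharge day

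*Combined protocol and SAP*

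**What the plan says.** **Question.** The PICO statement in section 1.0 asks whether a second block can "more effectively wean patients off postoperative opioids during the inpatient stay". Section 2.0 adds the expectation that it will "reduce the total postoperative OME".

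**Primary endpoint.** Section 1.0 states: "The primary outcome measure will be the initial discharge opioid prescription volume of patients in each arm". Under Decision on Discharge Opioid Prescription in section 4.0, the prescription is formulaic: "we will use a multiplier of 5x the last-24hrs OME count". The count "will be taken from the time of final discharge prescription writing".

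**Secondary outcomes.** The hospital measures are zero discharge OME, MDASI-GI, daily pain scores, and length of stay with cost. The discharge measures include 30-day total OME and the number of days until opioid use reaches zero. Section 5.0 plans a linear mixed model for daily pain scores and names no model for daily opioid use.

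**Setting.** The trial is open label, and allocation is unmasked on the morning of POD3. Section 4.0 says "There will be no standardization of postoperative dietary advancement, fluid management, or postoperative care", with an exception for the non-opioid bundle and the initial IV-PCA settings. No discharge criterion is given, and adequacy of pain control before discharge is judged without a threshold score.

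**The concern.** Because of the 5x rule, the primary endpoint is a rescaled measure of inpatient opioid use on one day, the last before the prescription is written. That day is not fixed in postoperative time. It moves with length of stay, which treatment may affect and which unmasked clinicians decide.

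If opioid need falls as patients recover, an arm kept longer will show a lower discharge OME even when its daily OME curve is identical to the other arm's. Conversely, an arm that weans faster and leaves sooner can have part of its benefit hidden.

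The 5x rule removes discretion over the size of the prescription given the count, but not over when the count is taken. The authors recognise that window timing matters, since they specify that for a POD4 discharge the count follows the block. They address it for that day only.

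At stake is the interpretation of the result. The trial can show that one strategy sends patients home with less opioid, yet have no direct measurement showing that inpatient weaning was the reason.

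**Working it through.** **1. Reproducing the plan's figures (section 5.0).** Inputs: means 200 and 75 mg, common SD 200 mg, two-sided alpha 0.05, power 81%, 1:1 allocation, 20% dropout.

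- n per arm = 2 x (1.960 + 0.878)^2 x (200/125)^2 = 2 x 8.05 x 2.56 = 41.2, rounded up to 42, so 84 in total.
- Power at 42 per arm: 81.7% (normal) and 80.8% (noncentral t), against 81% stated.
- Dropout: 42/0.80 = 52.5, rounded up to 53 per arm, so 106 enrolled.

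The sample size reproduces, and this point does not change it.

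**2. What the endpoint measures.** Dividing by the multiplier of 5, the design means correspond to last-24-hour inpatient OME of 200/5 = 40 mg and 75/5 = 15 mg. The difference is 25 mg and the SD 200/5 = 40 mg.

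**3. No block effect, one arm discharged one day later.** Let d be the proportional daily fall in mean OME late in the stay. The documents give no value, so d = 10%, 20% and 30% are assumptions, as is the one-day difference. The SD is held at 200 mg. The shift is 200 x d.

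| d | Shift (mg) | Share of 125 mg | Chance of p<0.05, 42 per arm |
|---|---|---|---|
| 10% | 20 | 16% | 7% |
| 20% | 40 | 32% | 15% |
| 30% | 60 | 48% | 27% |

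Without the timing difference, that chance is 5%.

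**4. Block works as designed, intervention arm discharged one day earlier.** The intervention mean becomes 75/(1 - d).

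| d | Intervention mean (mg) | Difference (mg) | Power |
|---|---|---|---|
| 10% | 83.3 | 116.7 | 75% |
| 20% | 93.8 | 106.2 | 67% |
| 30% | 107.1 | 92.9 | 56% |

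Without the timing difference, power is 81%.

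**5. Would the interim length-of-stay check catch this?** Section 4.0, Safety Review, stops the trial if the intervention median stay is at least 25% longer, assessed once at 42 randomised. A one-day prolongation is 1/4 = 25% of a four-day control median, which triggers the rule, but 1/5 = 20% of a five-day median, which does not. The documents give no length-of-stay figure, but patients expected to leave on or before POD4 are excluded. The check is also one-directional, so it cannot detect earlier discharge in the intervention arm.

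**The case against.** Several points stand against a stronger reading.

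- A reader might infer that nothing in the plan measures inpatient opioid use. That is not so. The primary endpoint is itself derived from one inpatient day. Days until zero use is a weaning measure counted in postoperative days and not tied to discharge. The 30-day total may include inpatient days. However, the start of the 30-day window, the use that counts, and the handling of patients who never reach zero are all undefined.
- A reader might infer that discharge OME is the wrong primary endpoint. The documents do not support this. The primary objective and the PICO's own tagged outcome both name discharge volume, and the rationale concerns opioid reaching the community. In a pragmatic comparison, an effect that runs through discharge timing is legitimately part of the result.
- A reader might infer that a timing difference would go unseen. Length of stay is a secondary outcome compared by arm and is checked at the interim, so a sizeable shift would be visible. No planned analysis relates it to the primary endpoint, though, and because it arises after randomisation, simple adjustment would not be a clean remedy.
- Postoperative care is not wholly unstandardised. The bundle and initial PCA settings are fixed, and both arms follow published enhanced recovery protocols. A discharge criterion is still not stated.
- The sizes above need both an assumed daily decline and an assumed one-day difference in stay. Nothing in the documents shows that either will occur.

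**Conclusion.** The point holds as a gap in supportive measurement. It is not a flaw in the choice of primary endpoint. No outcome captures daily or cumulative inpatient OME after randomisation, although inpatient weaning is the PICO question and the plan itself notes: "This 24-hr count can be easily found in the electronic health record". Section 2.0 also reports a historical median total inpatient OME of 171 mg, so the site has already computed this quantity.

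A difference in discharge OME will answer the primary objective, but it cannot by itself be attributed to faster weaning. Under the assumed falls of 10% to 30% per day and a one-day difference in stay, 20 to 60 mg (16% to 48% of the design effect) could reflect timing alone, in either direction. These figures illustrate sensitivity and do not predict bias. The change is worth making because it is cheap and tests the stated mechanism directly.

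**What to change.** Keep the primary endpoint, its decision rule and the sample size. Add the following from the health record, as supportive secondary outcomes or descriptive reporting:

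1. **Daily inpatient OME from POD4**, analysed with the linear mixed model already planned for daily pain scores. Use POD3 OME as baseline, preferably the 24 hours up to randomisation because allocation is unmasked that morning. Include a sensitivity analysis for days missing because of discharge, since discharge depends on recovery.
2. **OME in fixed postoperative windows**, identical in both arms. State that windows within 72 hours of the block, up to about the morning of POD7, reflect active analgesia as well as weaning. Later windows avoid this but will be less complete.
3. **Beside the primary result**, report by arm the postoperative day of the 24-hour window and the length of stay. Report cumulative OME to discharge only alongside length of stay, on which it depends.
4. **Define the existing measures.** Count days to zero from surgery, treat patients who never reach zero as censored, and use a time-to-event analysis instead of the t-test. State when the 30-day total starts and whether inpatient days count.

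Do not make the trial's conclusion conditional on the fixed-window result agreeing with the primary. That would add a second hurdle whose power has not been assessed.

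The cost is some data extraction, extra analyses, and incomplete data for patients discharged early. No additional patients or procedures are needed.

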2.0 Rationale

There is increasing evidence that an elective surgical event is often a patient's initial and greatest exposure to opioids.¹⁻³ In survivors of cancer surgery, persistent opioid use can be predicted by the dispensed volume of a patient's initial outpatient prescription at surgical discharge.^{1,4,5} Furthermore, national prescribing pattern data have shown that the initial outpatient prescription of *oral morphine equivalents (OME)* can be predicted by opioid utilization during the last 24hrs in the hospital.^{6,7} A tangible contribution from the surgical community would be the active implementation of a protocol to eliminate or reduce outpatient opioid dissemination in a greater proportion of cancer survivors after oncologic surgery. In this context, we have implemented regional anesthetic techniques including ultrasound-guided four-point *bilateral quadratus lumborum (QL) block using 72-hr liposomal bupivacaine*. Despite the hospital-wide emphasis on enhanced surgical recovery principles to reduce hospital length of stay, opioid reduction has not been a focused tenet of our enhanced surgical recovery goals until recently. In a recent analysis of five commonly performed Index operations from our Department of Surgical Oncology (including sarcoma resection), only 5% of our patients were discharged without opioids.

We thus see an opportunity to accelerate postoperative opioid weaning to reduce the total opioids used in the postoperative setting with the downstream effect of having less patients using opioids past the initial recovery period (characterized in literature as “persistent use”). We hypothesize that a second, repeat QL block on postoperative day 4 will bridge the gap between the initial intraoperative QL block and ambulatory status, reduce the total postoperative OME, and increase the proportion of sarcoma survivors free of opioids beyond the postoperative recovery period. **“Rescue blocks” are currently used on an as-needed basis** only when the first block is insufficient or if the clinical team decides that the opioid use is subjectively too much. Until recently with our **“RESQU-BLOCK” trial** (PA18-0859, NCT03745794), we had not been routinely using a 2nd block, because opioid-free discharge has never previously been a goal, even with enhanced surgical recovery protocols. However, with the successful implementation and enrollment of the RESQU-BLOCK trial (similar goals as this trial except in pancreatectomy, with first enrollment 3/1/2019), our new long-term goal is to **reduce dissemination of opioids into the community and reduce the risk of persistent opioid use among survivors, their families, and their communities.**

“Enhanced recovery after surgery,” or ERAS, is no longer a novel idea. However, its benefits are beginning to be seen beyond the early metrics of hospital stay and activities of daily living. Downstream benefits have included reduced complications, fewer readmissions (despite earlier discharges), less hospital resource consumption (cost), and improved postoperative quality of life. With the opioid epidemic increasingly discussed in both medical

and lay literature, we are seeking to modify our enhanced recovery program in abdominal cancer surgery to reduce opioid exposure in the hospital. Medical literature has shown that oftentimes the first exposure or greatest exposure to opioids comes from an elective surgical event. Persistent opioid use can be predicted by the size of a patient's initial outpatient prescription **oral morphine equivalents (OME)** and the initial outpatient prescription OME can be predicted by the amount of opioids used in the last 24hrs of hospitalization, which is often the result of how quickly the inpatient pain medications are weaned.

We recently analyzed opioid prescription patterns for patients who underwent major surgery in 5 major disease sites within Department of Surgical Oncology from March 2016 to April 2018, and one of these disease sites was sarcoma. A total of 192 patients underwent an operation for sarcoma with a median total inpatient OME of 171 mg (IQR 80-375 mg). Moreover, patients undergoing sarcoma surgery received a median of 300 mg OME (IQR 200-608 mg) at discharge, which was the 3rd highest of those analyzed. This revealed that discharge prescription OME after sarcoma surgery were paradoxically **higher than** their median **total inpatient OME** use after surgery. **They received more opioids at discharge than they used in the entire hospitalization.** Notably, across the entire surgical oncology patient cohort, 23% of patients used zero opioids during the last 24 hours of hospitalization, yet the majority of these patients (83%) were still prescribed discharge opioids (median 210 mg, IQR 150-326 mg).

We thus see an **opportunity to reduce opioid exposure and accelerate the weaning process** to decrease the **volume of opioids disseminated to patients and the community in the critical early days after discharge.** We plan to implement an enhanced surgical recovery bundle for sarcoma patients by using standardized non-narcotics and reducing initial IV-PCA settings. This trial will help answer which arm (both within “usual care” parameters) will be better at reducing postoperative opioid use.

HYPOTHESIS

- We hypothesize that a **second, repeat QL block on postoperative day 4** will bridge the gap between the initial intraoperative QL block and ambulatory status, facilitating a rapid opioid wean and **thus decrease the volume of opioids used by sarcoma surgery survivors after index hospitalization.** Ultimately, this should reduce dissemination of opioids into the community and reduce the risk of persistent opioid use in survivors and diversion to families and communities.

